# 14.5.3 Reporting of Adverse Events to IRBs/IECs

All investigators shall report AEs, including expedited reports, in a timely fashion to their respective IRBs/IECs in accordance with applicable institutional regulations and guidelines. All IND Safety Reports to the FDA shall be distributed by DAIT/NIAID or designee to all participating institutions for site IRB/IEC submission.

### 14.6 Pregnancy Reporting

The investigator shall be informed immediately of any pregnancy in a study subject or a partner of a study subject. A pregnant subject shall be instructed to not stop taking IS study medication unless directed by his/her study physician. The investigator shall counsel the subject and discuss the risks of continuing with the pregnancy and the possible effects on the fetus. Monitoring of the pregnant subject shall continue until the conclusion of the pregnancy.

The investigator shall report to the SACCC all pregnancies within 1 business day of becoming aware of the event using the Pregnancy form. All pregnancies identified during the study shall be followed to conclusion and the outcome of each must be reported. The Pregnancy form shall be updated and submitted to the SACCC when details about the outcome are available. When possible, similar information shall be obtained for a pregnancy occurring in a partner of a study subject.

Information requested about the delivery shall include:

- Gestational age at delivery
- o Birth weight, length, and head circumference
- Gender
- Appearance, pulse, grimace, activity, and respiration (APGAR) score at 1 minute, 5 minutes, and 24 hours after birth, if available
- Any abnormalities.

Should the pregnancy result in a congenital abnormality or birth defect, an SAE shall be submitted to the SACCC using the SAE reporting procedures described above. Pregnancies reported as SAE's will be reported as expedited events to the FDA as described above.

### 14.7 Reporting of Other Safety Information

An investigator shall promptly notify the site IRB as well as the SACCC using the AE/SAE form when an "unanticipated problem involving risks to subjects or others" is identified, which is not otherwise reportable as an AE.

# 14.8 Review of Safety Information

The PI, the NIAID medical monitor, and the NIAID DSMB will review safety data on an ongoing basis. Enrollment and initiation of study treatment may be suspended at any time if any of these reviews conclude that there are significant safety concerns.

In addition to the dose escalation plan (Section 5.4), the SACCC will continuously monitor accumulating safety data to determine if any of the following criteria are satisfied. If a criterion is satisfied, the trial will be placed on hold pending DSMB review, during which event rates and other clinical data will be evaluated. During this holding period, screening, enrollment, and initiation of any new study treatment or procedure will cease. Specifically, participants who are in Stage 1 will not be allowed to initiate Stage 2 and participants in Stage 2 will not be allowed to initiate Stage 3. However, participants who have received Thymoglobulin® will be allowed to proceed to EVR conversion unless specifically disallowed by the Medical Monitor.

# 14.8.1 Study Stopping Rules

The decision to pause enrollment pending DSMB review will be based on the occurrence of selected SAEs described below:

1. Death or graft loss

Confidential Page 61 of 80

- 2. Infections of Grade ≥3 as defined in Section 14.3.1
- 3. Severe AR
  - a. Histological: according to 1997 Banff criteria (Demetris A. D., 2000)
  - b. Clinical: steroid refractory rejection (see Study Definitions)
- 4. CR (early or late) according to 2000 Banff criteria (Demetris A. J., 1997)
- 5. PTID
- 6. Malignancy excluding recurrent HCC and skin cancer
- 7. CTCAE  $\geq$  3 Infusion reaction
- 8. Failure to manufacture and supply the cellular product for 2 subjects.

Since the trial is small and these events are of particular concern, and the risks are expected to be different in the two stages of the trial, absolute thresholds for the numbers of such events have been established for each event in each stage that would satisfy the stopping rule.

Table 7. Minimum Numbers of Selected AEs in each Stage that would Satisfy the Stopping Rule

Selected SAE	Lymphocyte Depletion/Treg Supportive IS Stage 2	darTreg Infusion Stage 3
Death or graft loss	1	1
Grade ≥3 Infection (Section 14.3.1)	1	1
Severe AR (histological or steroid refractory rejection)	2	1
CR	1	1
PTLD	1	1
Malignancy excluding recurrent HCC and in situ skin cancer	1	1
CTCAE ≥ 4 Infusion reaction	N/A	1

Every patient who initiates Stage 2, defined as receiving any amount of a Thymoglobulin® infusion, will contribute to the assessment of the safety of Treg supportive IS. At the point in time when the patient initiates Stage 3, defined as receiving any amount of a darTreg infusion, he/she will contribute to the safety assessment for darTreg infusion. Any death or Grade ≥3 infection (defined in Section 14.3.1) occurring in subjects prior to initiation of Thymoglobulin® infusion (prior to Stage 2) will not stop the trial.

The UCSF HICTF, NIAID MM, and study PI will review available information after the first instance of the dose falling short of target range, and again in the event of a second product not meeting the specified dose. If a pause is required due to manufacturing failures, one subject will be allowed to receive study directed Thymoglobulin during the review process. Recruitment and enrollment activities can continue during this time. If a third instance of lower-than-expected dose is manufactured, the study will be paused and DSMB will review available data prior to the trial proceeding.

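### Protocol 14.8.1: the event list and Table 7 define two single-event stopping triggers differently (infusion reaction Grade ≥3 or ≥4; all or only in situ skin cancer excluded)

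*Protocol*

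**What the plan says.** Protocol Section 14.8 makes the stopping rules binding: "If a criterion is satisfied, the trial will be placed on hold pending DSMB review". During a hold nobody new is screened or enrolled, and no new study treatment or procedure starts.

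Section 14.8.1 then sets out the triggers in two forms.

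- **The numbered list.** It is introduced as "selected SAEs described below". Item 6 is "Malignancy excluding recurrent HCC and skin cancer". Item 7 is a CTCAE grade of at least "3 Infusion reaction".
- **Table 7.** Its title is "Minimum Numbers of Selected AEs in each Stage that would Satisfy the Stopping Rule", although its first column is headed with SAEs rather than AEs. Its malignancy row is "Malignancy excluding recurrent HCC and in situ skin cancer", with a threshold of 1 in Stage 2 and 1 in Stage 3. Its infusion row is "CTCAE ≥ 4 Infusion reaction", not applicable in Stage 2 and with a threshold of 1 in Stage 3.

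The sentence joining the two says that "absolute thresholds for the numbers of such events have been established for each event in each stage that would satisfy the stopping rule".

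The SAP sets no thresholds of its own. Its Section 7 sends the reader to protocol Section 18.3.1 for the stopping rules, a number that does not exist in the current protocol.

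**The concern.** A stopping rule that acts on one event has no other moving part: the event definition decides the outcome. Here two definitions sit side by side in the same section. When a serious Grade 3 infusion reaction or a serious invasive skin cancer occurs, the coordinating center, which must monitor the criteria continuously, can read the text as requiring a hold or as not requiring one.

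The point reaches beyond the hold. Sections 5.4.1 and 5.4.2.2 refer cohort progression to Section 14.8. Section 5.4.2.2 also cites it for the safety signals that the four-week wait after each cohort's first infusion is meant to rule out. In a dose escalation of a product that Section 1.4 describes as new to humans, the trigger should be settled before the event, not argued afterwards.

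**Working it through.** The plan states no operating characteristics for the stopping rule, so there is no figure to reproduce. The check is a comparison of the texts, followed by an illustration of size.

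**1. The two texts side by side**

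| Event (serious) | List, 14.8.1 | Table 7 | Threshold in Table 7 |
|---|---|---|---|
| Grade 3 infusion reaction | counts (item 7, Grade ≥3) | does not count (Grade ≥4) | 1, Stage 3 |
| Invasive skin cancer | does not count (item 6, all skin cancer excluded) | counts (only in situ excluded) | 1, Stage 2 or Stage 3 |

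Table 7 has 7 rows, and 2 of them conflict with their list items.

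**2. Can a general reading rule settle it?**

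- *Take the stricter source.* The list is stricter on infusion reactions and the table on malignancy, so this does not select one source.
- *Let Table 7 govern.* Its title supports this. The joining sentence does not: it presents the table as giving counts of the listed events, not new definitions.
- *Let the list govern.* Its lead-in ties the pause directly to the listed events, but nothing gives the list precedence either.

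**3. Evidence elsewhere in the documents**

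- Infusion reaction: Grade ≥3 is used in safety outcome 5 (protocol 3.2) and in the rule for stopping an individual infusion (protocol 7.2).
- Malignancy: skin cancer is excluded without qualification in protocol 7.1 and in the SAP 9.3 displays.

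On both events Table 7 is the odd one out. Those passages serve other purposes, however (outcomes, individual discontinuation, displays), so they suggest intent without fixing it.

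**4. Which reactions are affected**

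Both the list lead-in and the Table 7 column header speak of SAEs, so a non-serious Grade 3 reaction may trigger neither. The planned 24-hour stay after infusion (5.1.2) does not by itself make a reaction serious, because admissions for protocol procedures are not collected as AEs unless complications prolong them (14.4.3). The illustration below therefore concerns serious Grade 3 reactions only.

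**5. Illustration of size (assumed rates)**

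Infused subjects, from the synopsis and Section 5.4.1: Cohorts 2 and 3 with 3 to 6 each and Cohort 4 with 6.

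- Minimum: 3 + 3 + 6 = 12
- Maximum: 6 + 6 + 6 = 18

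The chance of at least one serious Grade 3 reaction, at per-subject probability p, is 1 − (1 − p)^n.

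| Assumed p | n = 12 | n = 18 |
|---|---|---|
| 2% | 1 − 0.98^12 = 0.215 | 1 − 0.98^18 = 0.305 |
| 5% | 1 − 0.95^12 = 0.460 | 1 − 0.95^18 = 0.603 |
| 10% | 1 − 0.90^12 = 0.718 | 1 − 0.90^18 = 0.850 |

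The two wordings can also be compared directly. Take n = 12, an assumed 1% rate of serious reactions of Grade 4 or higher and an assumed 5% rate at Grade 3. The chance of an infusion-reaction hold is then 1 − 0.94^12 = 0.524 under the list and 1 − 0.99^12 = 0.114 under Table 7.

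These figures ignore holds that another row may already have triggered. The documents give no skin-cancer rate, and that part is not quantified.

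**The case against.** The best counter-argument is that Table 7 is plainly the operative test. Section 14.8 acts when a criterion is met, and for the clinical events only the table gives counts by stage. The list cannot work alone: severe acute rejection needs 2 events in Stage 2 and 1 in Stage 3, which appears only in the table. On this view the list names event types and the table decides. The reading is plausible, but no text states it, and the joining sentence points the other way. Even if it is right, item 7 and item 6 are then wrong and need correcting.

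The second argument is that little turns on the conflict in practice. Much of this stands. A Grade ≥3 reaction stops that subject's infusion (7.2), SAEs are reported within 24 hours (14.5.1), and the principal investigator, medical monitor or DSMB may suspend the trial at any time (14.8). The second infusion in each cohort waits four weeks after the first (5.4.2.2, 5.4.3), and SAP Section 7 sends the DSMB any event that could contribute to a stopping rule. Escalation rests on cumulative AEs, not on this row alone. But these safeguards either depend on judgment or ensure only that the event is noticed. An automatic rule exists so that the pause does not depend on judgment after the fact.

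The third argument is that the assumed rates are unsupported. That is fair. The nearest experience in the protocol (Section 1.4) is 14 subjects given polyclonal Tregs, with no Grade 4 or 5 AEs and three SAEs, none judged more than unlikely to be related. It is a different product and a small sample: 0 of 14 leaves a one-sided 95% upper limit of 1 − 0.05^(1/14) = 0.193, so a 10% rate is not excluded. The 18-subject column also requires both Cohorts 2 and 3 to expand, while Section 15.6 plans for up to 12 infused.

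Finally, the skin-cancer conflict needs a serious invasive tumor within 40 weeks of transplant, and its effect on the SAP is small. Such a case would be absent only from the special display in SAP 9.3, not from the AE tables or, being serious, the SAE listings. The AE/SAE wording is largely editorial.

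**Conclusion.** The concern holds. Section 14.8.1 contradicts itself in current, legible text on 2 of 7 table rows, each with a single-event threshold, and neither document says which version governs. For a serious Grade 3 infusion reaction or a serious invasive skin cancer, the automatic hold depends on which line is read.

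The conflict itself rests on the text alone. Its practical size rests on assumptions: at per-subject rates of 2% to 10%, the chance that a serious Grade 3 reaction occurs at all is 22% to 72% with 12 infused subjects and 30% to 85% with 18. No estimate, confidence interval or analysis set is affected. The infusion-reaction conflict is the more important of the two. This should be fixed: it is a conflicting decision threshold that protects subjects, and the correction is cheap.

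**What to change.** Use one definition per event in both the list and Table 7.

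- **Infusion reaction.** Change Table 7 to Grade ≥3, which agrees with item 7, safety outcome 5 and Section 7.2. A higher grade for a trial-wide hold is also coherent. If the sponsor and DSMB intend Grade ≥4, change item 7 instead.
- **Malignancy.** Choose one skin-cancer exclusion and apply it in item 6, Table 7 and SAP 9.3. Excluding only in situ disease is more protective, but item 6, Section 7.1 and SAP 9.3 all use the broader exclusion, so the sponsor should confirm which is meant. Section 7.1 gives general reasons for stopping an individual's regimen and can stay or be aligned.
- **Seriousness.** Add one sentence saying whether a trigger must be an SAE, and use the same term in the list lead-in, the table title and the column header.

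The cost is one protocol wording amendment: a line for each event and a sentence on seriousness. SAP 9.3 changes only if the in situ wording is chosen. No extra subjects or data are needed. Choosing Grade ≥3 may add a pause for DSMB review.

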#### 3.2 Safety Outcomes

The safety, tolerability, and ties of darTreg therapy given within the context of either a TAC- or EVR-based IS regimen will be evaluated with the rate of the following events within 40 weeks of transplantation:

Clinical outcomes that will be described are:

- 1. Incidence and severity of biopsy-proven AR and/or CR (Demetris A. J., 1997) (Demetris A. D., 2000)
- 2. Incidence of ≥ Grade 3 infections as defined in Section 14.3.1
- 3. Incidence of wound complications (≥ CTCAE Grade 3)

Confidential Page 30 of 80

- 4. Incidence of anemia, neutropenia, and/or thrombocytopenia (according to study defined reporting requirements, *Section 14.3.1*)
- 5. Incidence of AEs attributable to the darTreg infusion including infusion reaction / cytokine release syndrome (CRS) (≥ CTCAE Grade 3), and malignant cellular transformation.

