#### 5.1.2 Dosage, Preparation, and Administration

Confidential Page 36 of 80

The deuterium-labelled darTreg product will be transported within UCSF and between UCSF and remote clinical centers in a shipping container with a temperature monitor and a coolant pack(s) to maintain the temperature between 2°C and 10°C. The product should be maintained in the shipping container until its administration. The infusion of the product must occur within 30 hours after final formulation. The identity of the donor, recipient and the product will be verified by two individuals prior to infusion.

Subjects meeting eligibility criteria for darTreg infusion will receive a single IV dose containing 50 (range 25-60), 200 (range 100-240), or 800 (range 400-960) million darTregs administered in approximately 20-30 minutes by gravity. The line will be primed with saline prior to infusion and the product bag, tubing, and peripheral IV line will be flushed with up to 250ml normal saline to ensure the complete dose is infused.

Pre-medications will be administered prior to infusion (see Section 6.2.2).

Vitals signs will be monitored before, during, and after the infusion. Emergency medical equipment will be available during the infusion in case the subject has an allergic response or an infusion reaction that can result in a CRS. The IV line will be maintained after the infusion and the subject will be asked to remain in the clinical research unit for a minimum of 24 hours which will allow ongoing monitoring for any infusion-related signs and symptoms.

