### 7.2 Premature Discontinuation of darTreg Infusion

darTreg infusion will be stopped and will not be restarted if there is a hypersensitivity reaction, a CTCAE Grade  $\geq$ 3 infusion-related reaction, a CTCAE Grade  $\geq$ 3 CRS, or any other infusion related serious adverse event.

Confidential Page 44 of 80

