# 14.3 Grading and Attribution of Adverse Events

#### 14.3.1 Grading Criteria

The study site will grade the severity of AEs experienced by the study subjects according to the criteria set forth in the NCI-CTCAE — Version 4.0 for all AEs with the exception of Infection. The NCI-CTCAE manual provides a common language to describe levels of severity, to analyze and interpret data, and to articulate the clinical significance of all AEs. The NCI-CTCAE has been reviewed by the study investigators and has been deemed appropriate for the subject population to be studied in this protocol for all AEs with the exception of infection and hematologic events described below.

AEs will be graded on a scale from 1 to 5 according to the following standards in the NCI-CTCAE manual:

- Grade 1 = mild AE.
- Grade 2 = moderate AE.
- Grade 3 = severe and undesirable AE.
- Grade 4 = life-threatening or disabling AE.
- Grade 5 = death.

For any AE of Infection, the following grading system will be used for study participants:

- Grade 1 = asymptomatic; clinical or diagnostic observation only; intervention with oral antibiotic, antifungal, or antiviral agent only; no invasive intervention required
- Grade 2 = symptomatic; intervention with intravenous antibiotic, antifungal, or antiviral agent; invasive intervention may be required
- Grade 3 = any infection associated with hemodynamic compromise requiring pressors; any infection necessitating ICU level of care; any infection necessitating operative intervention; any infection involving the central nervous system; any infection with a positive fungal blood culture; any proven or probable aspergillus infection; any tissue invasive fungal infection; any pneumocystis jiroveci infection
- Grade 4 = life-threatening infection
- Grade 5 = death resulting from infection

Other than those described below, any events grade 2 or higher (including study defined grading of infections) will be recorded on the appropriate AE CRF for this study.

For hematologic events listed below, grade 3 or higher will be recorded on the appropriate AE case report form (CRF) for this study:

- Neutrophil count decreased
- Anemia (Hemoglobin decreased)
- Platelet count decreased
- Total lymphocyte count decreased
- Lymphocyte subset count decreased (including CD4)

Decreased CD4 lymphocytes and lymphocyte counts within 6 months after last study dose of Thymoglobulin® do not require reporting.

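### Protocol 14.8.1 gives two grades for the same automatic-hold event: a serious darTreg infusion reaction counts from Grade 3 in the list but only from Grade 4 in Table 7

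*Protocol*

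**What the plan says.** Under Protocol 14.8 the coordinating centre checks accumulating safety data continuously against set criteria. Once one is met, the trial stops until the DSMB has reviewed it. Screening, enrolment and new study treatment cease, and nobody in Stage 2 moves on to Stage 3.

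Section 14.8.1 sets the criteria in two steps. A list names the serious adverse events concerned. Item 7 is an infusion reaction of CTCAE Grade 3 or above (the printed item ends "3 Infusion reaction"). The text then says that "absolute thresholds for the numbers of such events have been established for each event in each stage", and Table 7 gives those counts. Its last row reads "CTCAE ≥ 4 Infusion reaction", with no threshold for Stage 2 and a count of 1 for Stage 3. Both places are limited to SAEs: the list by its lead-in, the table by its column heading. Neither mentions CRS.

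Section 14.3.1 shows what the one-grade gap means: "Grade 3 = severe and undesirable AE" against "Grade 4 = life-threatening or disabling AE".

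Three other places bear on the point:
- Section 7.2 ends an individual's infusion for a Grade 3 or higher infusion-related reaction and, as a separate ground, for Grade 3 or higher "CRS, or any other infusion related serious adverse event".
- Outcome 5 in Section 3.2 counts "infusion reaction / cytokine release syndrome (CRS) (≥ CTCAE Grade 3), and malignant cellular transformation".
- Section 5.1.2 speaks of "an infusion reaction that can result in a CRS".

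Sections 5.4.1 and 5.4.2.2 tie progression between cohorts to the adverse events described in 14.8.

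**The concern.** An automatic hold is useful only if the people applying it can tell, without judgement, whether it has been met. Here the coordinating centre has two instructions for the same event. After one serious Grade 3 reaction in Stage 3, the list calls for a hold and the table does not.

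The stake is whether the next participants are infused before the DSMB has looked. Only the wait after the first infusion in each cohort is mandatory (4 weeks). The later 4-week gaps, including the one before the first infusion of the next cohort, are recommended only (Section 5.4.2.2). Doses rise fourfold at each step, from 50 to 200 to 800 million cells, so a hold that was meant to apply but did not could precede a higher dose.

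**Working it through.** **Step 1. Apply each rule to each kind of event in Stage 3.**

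| Event | List item 7 | Table 7 row | Same answer? |
|---|---|---|---|
| Serious Grade 3 infusion reaction | met | not met | no |
| Serious Grade 4 infusion reaction | met | met | yes |
| Grade 3 reaction that is not an SAE | not covered | not met | yes |
| Serious Grade 3 CRS, read as an infusion reaction | met | not met | no |
| Serious Grade 3 CRS, not so read | not met | not met | yes (no hold) |

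A fatal event of either kind meets the death row. The conflict is confined to serious Grade 3 events.

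**Step 2. Could the table merely add a count to the list?** No, because it changes the grade. The infection row, by contrast, keeps the list's Grade 3. List and table differ elsewhere too: for malignancy, the list excludes skin cancer while the table excludes only in situ skin cancer, and list item 8 (manufacturing failure) has no row. This suggests that the two were not kept in step, but it does not show which is right.

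**Step 3. Does other text settle it?** SAP Section 7 sends the reader to protocol Section 18.3.1 for the stopping rules. There is no such section; protocol 18.3 concerns privacy. Section 7.2 and outcome 5 use Grade 3, but one governs a single infusion and the other is a descriptive outcome. Neither decides the trial-level hold.

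**Step 4. Does it reach escalation?** Sections 5.4.1 and 5.4.2.2 cite 14.8 in general, not Table 7. The only list of adverse events within 14.8 is in 14.8.1. So it probably does.

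**Step 5. Illustrative size.** The plan gives no reaction rate and no operating characteristic for the rule, so there is no figure to reproduce. Assume a chance p per infusion, independent between infusions, that the worst acute event is a serious Grade 3 reaction. Then

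P(list and table disagree at least once in n infusions) = 1 − (1 − p)^n.

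The values of n follow from Sections 3.1 and 5.4.1: 3 + 3 + 6 = 12 as planned; 6 + 6 + 6 = 18 if Cohorts 2 and 3 expand. Before the first 800 million dose, n is 3 + 3 = 6, or 6 + 6 = 12 if expanded.

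| Assumed p | n = 6 | n = 12 | n = 18 |
|---|---|---|---|
| 2% | 11% | 22% | 30% |
| 5% | 26% | 46% | 60% |
| 10% | 47% | 72% | 85% |
| 20% | 74% | 93% | 98% |

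For example, 1 − 0.95^12 = 0.4596.

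**The case against.** **Table 7 may be the operative rule.** Its title and lead-in present it as what satisfies the stopping rule, with the list only selecting topics. Stopping one person's infusion at Grade 3 and the whole trial at Grade 4 would be a coherent tiered design. The protocol does tier elsewhere: all biopsy-proven acute rejection is an outcome, but only severe rejection is a hold event. This stands to the extent that a reader might call the table the error because 7.2 and outcome 5 use Grade 3, and the documents do not prove that. It does not remove the conflict, because the list still says Grade 3 for the same hold.

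**The event would not go unseen.** SAEs are reported within 24 hours (14.5.1) and go to the medical monitor (14.8.2). Suspension is possible at any time (14.8), and the DSMB can be called in ad hoc (14.8.3). SAP Section 7 goes further: the DSMB will review safety data after an event that could contribute to a stopping rule, and a listed Grade 3 reaction plausibly qualifies. All of this stands. None of it says that infusions stop during the review.

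**CRS is probably covered.** Sections 3.2 and 5.1.2 link CRS to infusion reactions, and Section 9.1 does so for Thymoglobulin. A reader might infer from 7.2, which lists CRS separately, that a severe CRS escapes the hold altogether. The documents lean the other way, so CRS is a missing clarification and not a second defect.

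**The assumed rates may be high.** Section 1.4 reports 14 adults given polyclonal Tregs with no SAE judged more than unlikely related, and 10 children with no toxicity noted. Taking that as 0 of 24, the one-sided 95% upper bound is 1 − 0.05^(1/24) = 11.7%. The product and patients differ, and the eight Grade 3 events among the adults are not itemised, so this is not an estimate for darTregs. It is reason enough not to lean on the 20% row.

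**Conclusion.** The inconsistency is real and should be fixed. It rests on the text alone: one hold event, two grades, and nothing to say which governs. It bites only for a serious Grade 3 darTreg infusion reaction, including CRS if read as one. Its consequence is uncertainty over whether new infusions must stop during review and, probably, over cohort progression. The percentages depend entirely on assumed values of p and on independence between infusions; they are not predictions.

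Three further inferences go beyond the documents:
- That any Grade 3 reaction meets the list. Only SAEs do, and the planned stay after infusion does not by itself make a reaction serious (14.4.3 excludes admissions for protocol procedures unless prolonged by complications).
- That escalation is certainly governed by the conflicting threshold. The reference to 14.8 is general, and 14.8 describes its monitoring as additional to the escalation plan.
- That this is the product's first use in humans. Section 1.4 says so, but 9.3.2 speaks of limited human experience and 4.4 mentions another trial of the same product. The point does not need it.

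**What to change.** Put the same text in list item 7 and the Table 7 row, preferably: 'serious CTCAE Grade ≥3 infusion reaction (including CRS)', Stage 2 not applicable, Stage 3 count 1. This is the more cautious choice and matches the grade in 7.2 and outcome 5. If the sponsor intended a tiered rule with a trial-level hold only from Grade 4, correct list item 7 instead and state the reason. Either choice resolves the conflict. The SAP's reference to Section 18.3.1 should point to 14.8.1 at the same time.

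The cost is a protocol amendment, which needs IRB, NIAID and FDA approval (18.1). If the table would otherwise have governed, the preferred wording can also add holds. The expected number of triggering events is n × p: at p = 5%, 12 × 0.05 = 0.6; at p = 10% with 18 infusions, 18 × 0.10 = 1.8. More than one extra hold is therefore possible. A hold bars entry to Stage 3, no length is stated for it, and the infusion window is 20 − 11 = 9 weeks, so a waiting participant could pass the week-20 limit and lose the infusion.
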